3.0 Purpose

The purpose is to evaluate the safety and effectiveness of Mobility+ enteral feeding system via this initial post-market study (510k clearance number K222678) in adults, a subset of the intended use population. This evaluation will be conducted in a prospective, single arm, non-randomized clinical study.

Hypothesis and Objectives

The study hypothesis is that Mobility+ meets its intended use, safely. The objectives are to evaluate the below primary and secondary endpoints, through execution of this protocol:

Endpoint	Detail	How it will be measured
Primary: Safety and Effectiveness of Mobility+	Evaluate participants who have received familiarization training can use device, according to IFU, to allow delivery of liquid nutrition to their feeding tube, in a real-life setting (home), safely (i.e. can execute critical device use tasks to allow feeding, without serious adverse events) and with effectiveness (i.e. using Mobility+ for the majority or all of their feeding sessions i.e. two daily feeds, minimum)	Phone communication and checklist (Appendix8)

Secondary: Usability of Mobility+	Evaluate Participant perspectives on mobility, ease of use and tolerance, with their current feeding system(s) and Mobility+	Participant perspectives surveys: Baseline (Appendix 4) End of study (Appendix 7)
	Evaluate changes in participant Quality of Life (QoL)	QoL survey at baseline (Appendix 5) and QoL question at end of study (Appendix 7)
	Estimate if participants consume similar average volume (and kcals) of feed/day during the study, compared to baseline	Collect descriptive data on estimated average feed volume and kcals consumed at baseline (Appendix 3) and at end of study (Appendix 8)

The outcome will be presented in a study report.

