8.6 Compliance

[figure not shown]
Phone communication surveys on Study days 7 and 14 will collect information on the amount participants are using, to capture if they are using Mobility+ for a minimum of 2 daily feeds (Appendix 8).

Note: In some cases, participants may not comply fully with their enteral feeding regime due to issues unrelated to the study or feeding system. At screening, potential participants will be asked how often they skip or cut-short feeding sessions to determine if general compliance with enteral nutrition (EN) feeding may be an issue. Questions on compliance will also be asked on Study Days 7 and Day 14 (See Appendix 8). Poor compliance (participants who take less than two daily feeds using Mobility+), should it occur, will be reported in the study results and sub analyses will be conducted on participants who met the criteria.

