		

How strongly do you agree with the following statement? I would like to use the Mobility+ again.

Strongly Agree	Somewhat Agree	Neutral	Somewhat Disagree	Strongly Disagree
				

If you would like to use Mobility+ again, how often would you like to use it?

Every Day	Every Week	Every Month
		

Think about your overall wellbeing if you used Mobility+ for SOME/ALL of your tube feeding needs, in the long term. How would your wellbeing be then, compared to now?

Much Better	Somewhat Better	About the Same	Somewhat Worse	Much Worse
				

Would you pay out of pocket for the Mobility+?

YES	NO
	

How did you choose to wear the Mobility+ system?

- Crossbody bag**
- Handbag**
- Backpack**
- In clothing**
- Clipped onto belt/clothing**
- Other (Detail):**

Appendix 8

Appendix 8 - Phone communication check sheet (Study Day 7 and 14) - (Operator asks the Participant these questions)

Day 7

Day 7			
Questions:	Answers:		
Day 7 Safety & Effectiveness Check			
Are you able to use Mobility+ to successfully and safely provide enteral feeding?	 YES  NO		
Day 7 Compliance & Calorie Intake Check			
Consider your feed intake over the last 3 days (i.e. Study day 4, 5, 6).			
Questions:	Answers:		
What volume of enteral nutrition did you consume on average per day (i.e. over 24 hr)?	Volume Mobility+mls		
How many hours did you typically infuse for, on average/day? hours minutes		
How many feedings did you intend to take using Mobility+ , on average / day?feedings		
How many feedings were you able to take using Mobility+ , on average / day?feedings		
What was the average volume of enteral nutrition that you consumed per feeding with Mobility+?mls		
What time of the day did you provide feedings with Mobility+?	Morning  Afternoon  Evening  Night-time 		
Operator facing question: On average, did the participant take at least two daily feeds with Mobility+? If no, why not?	 YES		
	 NO		
Day 7 Tubing SKU check			
Study Day 7:			
SKU that participant is using:			

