440mm RED 	700mm BLUE 	1000mm GREEN 	1900mm WHITE 

Select one:	Stay on this SKU 	Trial  SKU 
Reason for changing:	
Intolerance  Taking too long to feed  Abdominal discomfort  Unable to tolerate feed 
	

Day 14

Day 14 Tubing SKU Check			
What giving set tubing are you using?			
440mm RED 	700mm BLUE 	1000mm GREEN 	1900mm WHITE 
Day 14 Safety & Effectiveness Check			
Are you able to use Mobility+ to successfully and safely provide enteral feeding?	YES 	NO 	
Day 14 Compliance & Calorie Intake Check			
Consider your feed intake over the last 3 days (i.e., Study Day 11, 12, 13).			
What volume of enteral nutrition did you consume on average per day (i.e. over 24 hr)	Volumemls	Volume Other Systemmls	
How many hours did you typically infuse for, on average/day? hours minutes	
How many feedings did you intend to take using Mobility+, on average / day? feedings		
How many feedings were you able to take using Mobility+, on average / day? feedings		
What was the average volume of enteral nutrition that you consumed per feeding with Mobility+?mls		
What time of the day did you provide feedings with Mobility+?	 Morning  Afternoon  Evening  Night-time		

Safety and Effectiveness of A Novel Enteral Feeding System:
Prospective Study Protocol
Page 41 of 49

NCT06173063

Operator facing question:	On average, did the participant take at least two daily feeds with Mobility+?	YES 	NO 
	If no, why not?	

Appendix 9

Adverse event classifications

The below figures from ISO 14155:2020 highlight the process to be followed to determine if an AE or device deficiency is one of the below:

- AE
- SAE
- ADE
- SADE
- ASADE
- USADE
- Device deficiency with SADE potential
- Device deficiency without SADE potential

Table F.1 — Categories of adverse events

Adverse events	Non-device-related	Device- or investigational procedure-related	
Non-serious	Adverse event (AE) ^a (3.2)	Adverse device effect (ADE) ^c (3.1)	

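### Scoring two Mobility+ feeds a day secures majority use only below four sessions a day, so the reported 16/17 leaves that part of the primary endpoint undetermined

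*Protocol*

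**What the plan says.** Protocol 3.0 makes effectiveness one half of the primary endpoint and words it as "using Mobility+ for the majority or all of their feeding sessions i.e. two daily feeds, minimum", measured by the Appendix 8 phone check sheet.

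Every later step uses the count alone:

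- Inclusion criterion 5 (Protocol 8.4) requires that at least two feeds a day can be moved to Mobility+. It sets a floor and no ceiling on sessions.
- Protocol 8.6 says the Day 7 and Day 14 calls are "to capture if they are using Mobility+ for a minimum of 2 daily feeds", and calls anything less poor compliance.
- In Appendix 8 the operator's yes/no item on both days opens "On average, did the participant take at least two daily feeds with Mobility". The form also asks "How many feedings were you able to take using Mobility+, on average / day". It does not ask for total sessions. That number is requested once, at screening (Appendix 2 Q5).
- Appendix 8 also carries a separate yes/no safety and effectiveness check on whether the participant can feed successfully and safely.

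SAP 7.0 reports both items for 17 participants: 17 (100%) on the safety and effectiveness check and 16 (94.1%) on the two-feed rule. SAP 3.0 gives 19 as the number included. The SAP shows no distribution of sessions per day or of Mobility+ feeds per day, and does not say whether the 16 refers to Day 7, Day 14 or both.

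**The concern.** The endpoint sentence treats a share and a count as the same thing. They agree only if participants have few enough sessions, and the protocol never sets that condition. A participant with four or more sessions can satisfy the scored rule with two Mobility+ feeds while taking half or more of their sessions on another system. Mixed use is foreseen: the Day 14 form has the field "Volume Other Systemmls".

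At stake is what the headline effectiveness figure may be taken to mean. Someone who reads the endpoint in Protocol 3.0 and then the 94.1% in SAP 7.0 could conclude that 94.1% used Mobility+ for most of their feeding. Nothing in the SAP establishes that.

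**Working it through.** **1. Reproduce the SAP figures.** SAP 3.0: 548 − 493 − 11 − 25 = 19 included. SAP 7.0: 17/17 = 100% and 16/17 = 94.1%. All agree with the text.

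**2. When does the count imply a majority?** Let S be total sessions per day, and take majority as more than half. At exactly two Mobility+ feeds the share is 2/S, and 2/S > 1/2 only if S < 4.

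| Sessions per day | Share at exactly two feeds | Whole feeds needed for more than half |
|---|---|---|
| 2 | 100% | 2 |
| 3 | 66.7% | 2 |
| 4 | 50.0% | 3 |
| 5 | 40.0% | 3 |
| 6 | 33.3% | 4 |

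The shares are floors: the rule is at least two, so a participant who passes may have taken more.

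**3. Are four or more sessions excluded elsewhere?** The pouch holds 250 to 500 ml (Protocol 2.0), and Appendix 2 Q10 repeats the 250 ml minimum fill. Assuming equal feeds swapped one for one, four sessions imply at least 4 × 250 = 1000 ml/day, five 1250 ml and six 1500 ml. Inclusion criterion 4 sets a minimum of 500 ml/day and no maximum. The fill volume restrains the number of sessions but does not rule out four.

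**4. What does 16/17 then say about majority use?** Let m be the number of the 16 with four or more sessions and too few Mobility+ feeds for a majority. Those meeting both parts of the definition number (16 − m)/17. The documents give no value for m, so these are assumptions across its range:

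- m = 0: 16/17 = 94.1%
- m = 1: 15/17 = 88.2%
- m = 4: 12/17 = 70.6%
- m = 8: 8/17 = 47.1%
- m = 16: 0/17 = 0%

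The extremes are logical bounds, not estimates.

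**5. Denominator.** Two of the 19 included have no reported outcome. If neither met the two-feed rule, 16/19 = 84.2%; if both did, 18/19 = 94.7%.

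**6. Can volume stand in for sessions?** Two pouch feeds are 2 × 250 = 500 ml to 2 × 500 = 1000 ml. The documents report no total daily volume. At an assumed 1000 ml/day, the two feeds are 50% to 100% of volume; at an assumed 1500 ml/day, 33.3% to 66.7%. The same two sessions can fall on either side of one half, so volume share is only a proxy.

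**The case against.** The strongest reply is that the protocol defines its own term. The endpoint sentence ends by equating majority with two feeds. The same count appears in the inclusion criteria, the compliance section, the screening questionnaire, both calls and the SAP row. On that reading the endpoint was scored as operationalised and 16/17 answers it. This stands, but it leaves the majority-or-all wording with no force at four or more sessions, so the sentence still needs reconciling.

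Three further points also stand. Neither document describes 94.1% as majority use. No document shows any participant with four or more sessions. SAP 6.0 and 7.0 are headed as supplemental, and Protocol 3.0 sends the outcome to a study report that is not available here, so silence in the SAP does not prove the figure was never produced.

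A reader might infer that the 94.1% is wrong or that the effectiveness endpoint was missed. The documents do not support this: the row states exactly what was counted, and those who passed may have taken more than two feeds. A reader might also infer that the rule errs the other way, failing someone who averages 1.5 of 2 feeds. That does not hold, because the endpoint itself sets two daily feeds as the minimum.

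**Conclusion.** The point holds as a gap between the endpoint's wording and what was scored. Meeting the two-feed rule guarantees majority use only below four sessions a day, entry does not secure that condition, and the form named for the primary endpoint does not collect the denominator. The two SAP 7.0 rows are accurate under their own labels. Majority use is undetermined, and the number of the 16 affected may be zero.

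This rests on reading majority as more than half, and on the protocol and SAP alone. The threshold of four is exact; the practical size is unknown. The matter should be corrected because it concerns the primary effectiveness claim of a single-arm study and can largely be addressed from fields already on the forms.

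**What to change.** 1. State, labelled as a clarification made after results, that effectiveness was scored as at least two Mobility+ feeds a day. Reconcile this with the majority-or-all wording in Protocol 3.0, and do not interpret 94.1% as majority use.
2. Keep 16/17 under its present label. Say whether it comes from Day 7, Day 14 or both, and show it against the 19 included, with the range in step 5 of the working.
3. Tabulate Appendix 2 Q5 sessions per day beside Day 14 Mobility+ feeds per day, descriptively and without a pass rate. Note that Q5 describes the system used before the study, and that the 500 ml pouch limit can change what counts as a session.
4. As a supporting post hoc figure only, give the number with more than 50% of Day 14 volume by Mobility+: Mobility+ volume / (Mobility+ volume + other-system volume).
   - First confirm on the original form that the Day 14 field reading only Volume means Mobility+. The matching Day 7 field reads "Volume Mobility+mls", and the table may be broken in the text version.
   - Cross-check it as feeds per day times the answer to "What was the average volume of enteral nutrition that you consumed per feeding with Mobility".
   - Label it a proxy for session share, give the recall window ("Consider your feed intake over the last 3 days (i.e., Study Day 11, 12, 13") and the number missing, and mark any total daily volume used in an example as an assumption.

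The cost is some wording, one small table and one descriptive proportion, with no new data collection. The downside is that the majority-use figure may be lower than 94.1% and will remain post hoc and approximate.

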8.3 Participants

This is a first in human post-market clinical study to evaluate the Mobility+ system, being carried out following market approval (i.e., FDA clearance). 25 participants will be enrolled to ensure data can be obtained for 20 participants (the expected drop-out rate is estimated at ~20%), as this is considered appropriate for a post-market clinical study on a low-risk device and will add meaningful data to device risk management files. If more than 5 participants drop out, re-recruitment will aim to bring the sample size up to 20.

Recruitment will aim to obtain a mix of female and male participants who meet the inclusion criteria. Screening questions will be used by operators during the recruitment process to ensure participants are eligible (See **Appendix 1** and **Appendix 2**).

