11.2 Data Analysis

Table 5 below details how data from the surveys will be analyzed.

Table 5: Details of how measurements will be analyzed

Measurement	General details on purpose of analysis	Specific details on analysis
Participant perspective surveys	Feeding system surveys at baseline and end of study, to assess participant perspectives on feeding system specific parameters and the impact of converting from usual system(s) to Mobility+	Surveys consist of 16 five-point Likert scale type questions, where rating options either range from very difficult to very easy, or strongly disagree to strongly agree. The ratings are assigned a point scoring system, whereby the most negative option (i.e. very difficult or strongly disagree) is assigned 0 points and the most positive option (i.e. very easy or strongly agree) is assigned 4, meaning the total possible maximum score is 64 points. As participants are asked to complete these surveys at baseline and at study end, the overall score obtained with their usual systems can be compared to the overall score obtained after using Mobility+. Scores for individual questions can also be compared.
QoL measures (QoL survey at baseline and QoL question at end of study)	A simple QoL measure will be used at baseline to gauge participants overall QoL using a scale previously published (See Appendix 5) accompanied by a simple question evaluating if self-perceived QoL has changed, at end of study	Determine baseline QoL Evaluate any changes to QoL in the second week of study

General End of Study Questions	
This survey is designed to assess changes in participants perceived wellbeing and mobility from study start – where they used their usual feeding system – to study end with Mobility+. It will also capture additional information on Mobility+ usage patterns and consumer demand for Mobility+.
	
The survey consists of 9 simple questions which predominantly assess change in participants perceived wellbeing and mobility with Mobility+ versus their usual systems. The questions are mostly Likert scale type questions where answer options range from “much better” to “much worse”. Additional questions assess the importance of mobility to the participant, how the participant wore the Mobility+ and if the participant would like to use the Mobility+ again, among others. Data collected will supplement QoL and participant perspectives data.

---------------------------------------	---	--

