3.0 Sample size

The aim was to recruit 25 participants, to allow for potential dropouts and obtain data for an ideal minimum of 20 participants. The number of patients who were screened was high, at 548. Of this 548, a high proportion (n= 493, 90%) were excluded as they did not meet the study criteria. Furthermore, 11 declined to take part, 25 did not take part for other reasons (e.g. did not show up to appointment or their clinical plan included intent to taper down enteral nutrition (EN) intake), resulting in 19 being the number of participants included. This was the highest number feasible to include in the time frame of the screening and close to the ideal minimum of 20 participants.

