5.0 Statistical test applied

The statistical test used was a paired T-test with ANOVA. Statistical significance was set at $P < 0.05$. Analyses were performed with IBM SPSS Statistics for Windows, version 29.0.1 (IBM Corp., Armonk, N.Y., USA).

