7.0 Supplemental Outcome data gathered

The following supplemental Outcome Data was gathered (n=17).

Compliance and Effectiveness (n (%))	
Successfully and safely feed with Mobility+	17 (100)
Achieved use of Mobility+ for minimum 2 daily EN feeds	16 (94.1)

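### 'Similar' daily intake is an endpoint without a criterion or confidence interval, and neither two cohort means nor a non-significant test could support the word at n=17

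*Protocol*

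**What the plan says.** Among the secondary endpoints in Protocol 3.0, one is to "Estimate if participants consume similar average volume (and kcals) of feed/day during the study, compared to baseline". The measurement column beside it reads "Collect descriptive data on estimated average feed volume and kcals consumed at baseline" and continues with the end of the study. No margin, range, interval or decision rule is attached.

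Protocol 11.2 introduces its analysis table with "Table 5 below details how data from the surveys will be analyzed". The table has rows for the perspective surveys, quality of life and the general end-of-study questions, and none for intake.

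SAP 4.0 scores mobility, ease of use and quality of life only. SAP 5.0 states "The statistical test used was a paired T-test with ANOVA" and sets significance at 0.05, without naming the outcomes tested or whether the test is two-sided. SAP 3.0 ends its account of recruitment with "resulting in 19 being the number of participants included", and the outcome table in SAP 7.0 is based on 17. The SAP shows no intake result.

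**The concern.** The endpoint has its conclusion built in: intake on the device is, or is not, similar to before. The plan gives no means of reaching that conclusion. If intake is handled descriptively, 'similar' rests on looking at two means. These carry no statement of precision and can hide individual shortfalls behind other participants' increases. If the SAP's test was applied to intake, a non-significant result could be taken for similarity, although it shows only that a difference was not detected.

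This matters because the device exists to deliver nutrition, and entry requires dependence on enteral feeding (at least 500 ml/day). The primary effectiveness criterion counts feeds per day, not volume, so this endpoint is the only planned comparison of intake with baseline. Protocol 8.7 starts participants on a giving set slower than their calculated average rate, and Appendix 8 lists excessive feeding time as a reason for changing it. A fall in volume is thus foreseeable enough to be worth measuring with an interval. That remark is about measurement and is no comment on the giving-set rule.

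**Working it through.** **The plan's own numbers.** Protocol 8.3 aims for 20 participants with data after about 20% dropout: 20 / (1 − 0.20) = 25, which matches the enrolment target. SAP 3.0: 548 − 493 − 11 − 25 = 19, which also matches. Neither document gives a power statement, SD, effect size or margin for intake, so there is nothing further to reproduce.

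**Inputs.** n = 17 (SAP 7.0), assuming all 17 have volume at both times. Significance level 0.05 (SAP 5.0), two-sided by assumption. The SD of the within-person change in daily volume is not in the documents; 150, 200, 300 and 400 ml/day are assumed, to show a range.

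**Precision.** The 95% CI half-width for a mean paired change is t(0.975, n−1) × SD / √n. At n = 17 this is 2.120 / √17 = 0.514 SD. At the planned 20 it would be 0.468 SD, so the shortfall in recruitment is not the main cause.

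**Power.** From the noncentral t distribution with 16 degrees of freedom and noncentrality (true loss / SD) × √17, 80% power needs a true change of 0.72 SD. For example, a true loss of 100 ml/day with SD 200 gives noncentrality 0.5 × 4.123 = 2.06 and power 49%, so a non-significant result in 51% of studies.

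| Assumed SD of change (ml/day) | 150 | 200 | 300 | 400 |
|---|---|---|---|---|
| 95% CI half-width (ml/day) | 77 | 103 | 154 | 206 |
| True change detectable with 80% power (ml/day) | 109 | 145 | 217 | 290 |
| Chance of P ≥ 0.05, true loss 100 ml/day | 27% | 51% | 75% | 84% |
| Chance of P ≥ 0.05, true loss 200 ml/day | 0.1% | 3% | 27% | 51% |

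**What a non-significant result leaves open.** The half-width is also the largest observed mean loss that stays non-significant. At that point the interval runs from zero to twice the half-width: 2 × 0.514 × SD = 154, 206, 308 or 411 ml/day.

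**What an interval criterion could deliver.** Take 100 ml/day purely as an illustrative limit, with no true change. The lower 95% limit would then lie above −100 ml/day in 73%, 49%, 25% and 16% of studies at the four SDs. Requiring the upper limit to be inside a range as well is harder still.

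**Whether the forms supply the data.** Appendix 2, question 4, asks for typical 24-hour volume and kcals at baseline. The Day 14 sheet in Appendix 8 asks for average daily volume over the previous three days, with a separate space for other systems. A paired change in total volume can therefore be computed. As shown, Appendix 8 has no kcal item, and Appendix 3, cited as the baseline source, has no intake item.

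**The case against.** The strongest reply is that this is a descriptive secondary aim, listed under usability, in a single-arm study sized for feasibility. The endpoint's verb is 'estimate', and such an aim does not need an equivalence margin or a powered comparison. That stands, and no powered equivalence study is called for. It does not supply a basis for the word 'similar', and an estimate is normally reported with its precision.

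Individual shortfalls are also partly visible elsewhere. Appendix 8 records feeds intended and taken, volume per feed, and reasons for fewer than two feeds. Protocol 8.6 commits to reporting poor compliance with sub-analyses. That is fair, but none of it compares volume with baseline.

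Three stronger readings are tempting and are not supported:

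- A reader might infer that the sponsor plans to read P > 0.05 as similar intake. SAP 5.0 names no outcome, and no passage says that non-significance will be interpreted in this way.
- A reader might infer that missing a real loss is the likely result. With an SD of 150 ml/day, a 200 ml/day loss would almost always be detected; with 400 ml/day it would be missed about half the time. The documents do not say which case applies.
- A reader might divide the half-widths for SDs of 200 to 400 ml/day by the 500 ml/day entry minimum and report undetected losses of 21% to 41%. That minimum is a floor, not mean intake; against an assumed mean of 1000 ml/day the figures are 10% to 21%. They are also limits for the observed mean loss, not the true one.

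**Conclusion.** The point holds in a limited form. 'Similar' intake is undefined, and on either reading of the analysis plan it could not be supported at n = 17. The firm figures are a 95% CI half-width of 0.51 SD and a detectable change of 0.72 SD. They rest on 17 complete pairs, a two-sided 0.05 level and approximate normality of the mean change. Everything in ml/day rests on an assumed SD. A mean loss of 100 to 200 ml/day can be missed, with a probability running from near zero to 84% across the range shown.

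The documents do not show that intake fell, that participants were harmed, or that the word 'similar' has been misused, since no intake result appears in the SAP. This is a cheap improvement that governs what may be concluded about a secondary endpoint. It is not a flaw in the design.

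**What to change.** In the SAP and the report:

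1. Compute each participant's change in total daily volume: Day 14 volume by Mobility+ plus other systems, minus baseline. Report the mean change with its 95% CI and the number of complete pairs, and list each participant's percentage change.
2. Do the same for kcals where they can be derived from the formula used. Say how they were derived, because Appendix 8 as shown does not collect them. Correct the cited source of baseline intake if Appendix 2 is the form actually used.
3. State which outcomes the paired test was applied to, and that P > 0.05 is not read as similarity.
4. Report the estimate and interval without the word 'similar', unless the whole interval lies inside a range that the sponsor states and justifies. The SAP is written in the past tense with outcome data in hand, so a range set after the data were seen should be labelled post hoc.

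The cost is one extra table and a few sentences, using volumes already collected. Justifying a range takes some further work, but only if the sponsor wants to keep the word. The real price is that the sponsor may be unable to claim similar intake.
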